#### Overview study plan.

Consecutive cervical cancer patients planned for robotic surgery, clinically stage 1A2 to 2A1.

Cervical injection of ICG and a total of 80 MBq Tc99 nanocolloid (the first 75 patients) and if the combination of nanocolloid and ICG after analysis better than ICG alone a continued combined use. If ICG or radiocolloid alone is equal or superior to the combined use in terms of technical success rates, the study will continue with the use of ICG or radiocolloid alone as tracer according to sample size analysis.

Registration of adverse events during insufflation and placement of port including necessary adhesiolysis.

Pelvic SLN identification with near infrared technique (and gamma probe first 75 patients) for identification of Indocyanine green (ICG) in lymphatics and lymph nodes. Ipsilateral cervical reinjection of ICG in case of non-display of any lymphatic pathway. Separate removal of the upper lymphovascular parametria. Registration of SLN- associated intraoperative adverse events.

Sentinel node in cervical cancer Version 1.2 180914 Frozen section of SLN and upper lymphovascular parametria.

A full pelvic lymphadenectomy after removal of SLN according to the Swedish National treatment protocol extended to the level of the inferior mesenteric artery in case of metastatic SLN's. Robotic Surgery with a Querleu Morrow B2 to C2 radical hysterectomy as appropriate or an aborted hysterectomy in case of metastatic SLN. Adnexal surgery as appropriate. Registration of associated intraoperative adverse events.

SLN's for ultrasectioning and immunohistochemistry. The remaining nodes for standard pathological bisectioning and staining with hematoxylin/eosine.

Registration of postoperative adverse events until 30 days after surgery using the Clavien Dindo classification.

Continuous data management. Analysis of technical success rates, sensitivity and false negative rates for SLN's comparing ICG with Radiocolloid after first 75 patients. In case of ICG + radiocolloid superior to ICG alone continued enrollment of patients using both tracers. In case of any of ICG or radiocolloid alone equal or superior to the combination continuation of the study for an interim analysis after 36 node positive patients (see section 11).

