#### **1. OBJECTIVES**

To estimate ICG and Radiocolloid alone and in combination to estimate any advantage of the combination of both tracers in terms of technical success rates/ bilateral mapping, sensitivity and false negative rates for the detection of pelvic SLN (first 75 patients).

To estimate the sensitivity and negative predictive value of the pelvic sentinel lymph node (SLN) concept for determination of lymph node metastases in patients with early stage cervical cancer planned for robotic surgery using either a combination of ICG and Radiocolloid or in case ICG alone is equal to or superior (in terms of technical success rate, bilateral mapping rates) to the combination the use of ICG as tracer for cervical injection using an anatomically based surgical algorithm and definition of sentinel lymph nodes.

To estimate if reinjection of tracer (ICG) will enhance the technical success / bilateral mapping rates.

To estimate the proportion of cervical cancer patients suitable for the SLN concept in conjunction with robotic surgery

To estimate complications associated with the detection and removal of SLN as such.

To estimate complications associated with ICG as tracer.

To estimate the incidence of lymphatic complications by the use of a validated questionnaire

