#### Technetium  Nanocolloid

The nanocolloid (GitPharma S.R.L. Saluggia Italy) will be prepared at the radionuclide unit at Skåne University Hospital, Lund, 1-2 hours before injection in four separate syringes each contacting 0,5mL and 20 MBq nanocolloid. The injection was performed the same was as described above and performed before the injection of ICG. A laparoscopic gammaprobe (Neo2000® laparoscopic probe, Neoprobe Corporation Dublin OHIO) will be used for detection of the SLN's defined by radiotracer.

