#### Sentinel node in cervical cancer Version 1.2 180914 5.0 TREATMENT PLAN

-Intraoperative cervical injection of Tc 99 nanocolloid and ICG (immediately before onset of surgery)

-Intraoperative lymphatic mapping and sentinel node identification with robotic NIR/fluorescence imager and gamma probe will be used for an initial transperitoneal, then retroperitoneal evaluation of display of ICG fluorescence/ radiopositivity. The retroperitoneal dissection with opening of the avascular planes saving the lymphatic vessels will start presacrally then further with the pelvic side walls. The upper lymphovascular parametria will be kept intact by a careful opening of the pararectal and paraveiscal spaces. -An ipsilateral reinjection of ICG will be performed in case of non-display of either of UPP or LPP. If the sentinel node cannot be identified in a particular pathway following a 15-20 minute search, the case should be described as a ICG-negative mapping event for that pathway. A initial scanning of the pelvic side walls and presacral area will be performed - A reinjection of ICG will be performed in case of non-display of the UPP and LPP bilaterally.

-The results of the lymphatic mapping will be marked on the anatomic plan and the specimens and labeling of those will be according to descriptions above.

-The complete SLN algorithm should be adhered to, i.e in case of a ICG negative mapping (for **SLN type 1 and 2, ICG defined**) and / or radio negative mapping any macroscopically metastase suspect nodes should be removed and defined as **SLN macro**. All patients will be subject for at least a full pelvic lymphadenectomy after removal of SLN.

-The upper lymphocascular parametrial tissue (the tissue medial of the obliterated umbilical artery, with the supravesical artery as distal/ventral border, the ureter as dorsal border and including tissue adjacent to the inner side of the broad ligament) will be removed and evaluated the same way as SLN's. This is to investigate the presence of lymph node in the upper parametria, theoretically the most juxtauterine nodes, hence the SLN.

-All SLN and the upper parametrial tissue will be subject for later ultrasectioning and IHC Histopathologic evaluation.

 In case of metastatic SLN the lymphadenectomy will be extended to the level of the inferior mesenteric artery and the hysterectomy aborted in favour of radiochemoptherapy. In case of a planned trachelectomy this will be transformed to

a radical hysterectomy.

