#### 7.0 STUDY CRITERIA

#### **Observations and Tests**

The following observations and tests are to be performed and, where appropriate, recorded on the designated form(s) (Appendix A):

PARAMETER	Pre-operative	Intraoperative	Postoperative
Log on approached patient	Х		
Log on included patients and	Х		
patients' withdrawal from study			
before surgery			
History & Physical examination	X		
Examination and evaluation by			
surgeon and anesthetist			
Laboratory test	Х		Х
Hb, S-electrolytes, S-kreatinine			
CRP, Trc, coagulation test when			
appropriate			
Injection data for ICG including	X	Х	Х
drug related adverse events			
		X7	
Sentinel nodes identification		Х	
Recording of intraoperative		X	
adverse events			

Sentinel node in cervical cancer Version 1.2 180914		
Histologic evaluation of sentinel		Х
nodes and non-sentinel nodes		
Decending of next on		Х
Recording of post-op		Х
complications until 30 days after		
surgery		
Recording of lymphatic		
complications on validated		
questionnaire at symptoms and at		
one year after surgery		

Adverse Events will be captured from time of ICG administration until30 days after surgery

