#### Adverse events related to the study drug (ICG).

All adverse events occurring from the first dose of study drug until hospital discharge (whether or not attributed to the study drug) will be reported on the Adverse Event Log. In addition, any adverse event reported by the subject to the investigator after discharge and determined to be reasonably associated with the study drug should also be captured and followed until resolution.

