#### Serious adverse event (SAE):

An adverse event that results in one or more of the following: -Any death occurring prior to the postoperative outpatient evaluation 30 days postoperatively. -Any life-threatening event until and including 30 postoperative days. -Any medical event requiring inpatient hospitalization or prolongation of existing hospitalization beyond five postoperative days

NOTE: Hospitalizations that are not considered SAE are:

-Hospitalization planned prior to first administration of study drug

-Hospitalization for elective treatment of a pre-existing condition unrelated to the study medication

- Hospitalization due to social / practical reasons such as an untimely coordination with local community home care services.

**Attribution:** Attribution is the determination of whether an adverse event is related to a medical treatment or procedure. The categories of attribution are:

Definite: The adverse event is clearly related to the study drug Probable: The adverse event is likely related to the study drug. Possible: The adverse event may be related to the study drug. Unlikely: The adverse event is doubtfully related to the study drug. Unrelated: The adverse event is clearly NOT related to the study drug.

**Unexpected Adverse Event**: An unexpected adverse event is an event not mentioned in the package insert/ manufacturer's instructions or the specificity or severity of which is not consistent with the package insert/ manufacturer's instructions. The grading described beneath and the attribution described above will be used for cathegorization of unexpected adverse events.

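### Adverse-event capture opens at the ICG injection and no form names the radiocolloid, although dual-tracer patients receive the radiocolloid first

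*Combined protocol and SAP*

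**What the plan says.** **Who receives both tracers.** The Overview study plan specifies "Cervical injection of ICG and a total of 80 MBq Tc99 nanocolloid (the first 75 patients"), and adds: "In case of ICG + radiocolloid superior to ICG alone continued enrollment of patients using both tracers". The same overview also allows continuation with either tracer alone, radiocolloid included. Section 1 names only the combination or ICG alone for the later phase.

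**Order and timing.** Under Technetium 99 Nanocolloid in Section 4.0, the radiocolloid injection is "performed before the injection of ICG" and follows the same technique. Section 5.0 places both together: "Intraoperative cervical injection of Tc 99 nanocolloid and ICG (immediately before onset of surgery"). The interval between them is not given. The ICG subsection asks for the injection time to be recorded. The nanocolloid subsection makes no such request of its own.

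**When capture starts.** Section 7.0: "Adverse Events will be captured from time of ICG administration until30 days after surgery". Section 10, under a heading that equates the study drug with ICG: "All adverse events occurring from the first dose of study drug until hospital discharge", irrespective of attribution.

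**How cause is coded.** The top attribution grade in Section 10 reads "The adverse event is clearly related to the study drug", and the other four grades also refer to the study drug. The title of Table 10.1 mentions the ICG injection but not the radiocolloid injection. The drug row of the SAE form in Appendix 1 names ICG.

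**What depends on it.** Section 1 lists the objective "To estimate complications associated with ICG as tracer".

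**The concern.** Two agents go into the same cervical sites, one after the other, but the safety rules are written as if there were only one. This has three possible effects.

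- The stated window opens after the first agent has been given.
- On the radiocolloid-alone branch, neither the window nor the attribution scale has anything to refer to.
- In dual-tracer patients the forms give the investigator no way to record the radiocolloid as the suspected cause.

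The objective at stake is the estimate of ICG complications. Section 4.0 puts ICG adverse effects below 1% and describes them all as allergic. With a rate that low, one event coded to the wrong agent is a visible share of the result.

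**Working it through.** The plan states no figure on this point, so there is none to reproduce. The check is a comparison of the text followed by simple proportions.

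**Step 1: what the literal window excludes**

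| Event starts | Section 7.0 window | Section 10, ICG events | Section 10, general definition |
|---|---|---|---|
| After radiocolloid, before ICG | Outside | Outside | Inside (any new medical problem in an enrolled subject, drug-related or not) |
| After ICG, up to discharge | Inside | Inside, whatever the attribution | Inside |
| Radiocolloid-alone branch | No start defined | No start defined | Inside |

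The first and third rows are contradictions within the plan. The second row shows that anything starting after ICG is captured.

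**Step 2: where a captured radiocolloid reaction can be coded**

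- On the attribution scale it can be graded for its relation to ICG, including as Unlikely or Unrelated.
- It can be logged as an event of the sentinel node procedure. Section 10 defines that class as excluding ICG-related events, and the SAE form has a row for it. The plan does not say whether radiocolloid injection belongs there.
- It cannot be recorded as related to the radiocolloid, because no grade, log or row names it.

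**Step 3: size of one miscoded event**

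Inputs: 75 dual-tracer patients (Overview study plan), 226 patients in stage 1 and 413 in total (Sections 9 and 11), and the quoted upper bound of 1% for ICG effects (Section 4.0).

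- Share of stage 1 receiving both tracers: 75/226 = 33%, or 100% if the combination continues.
- Rise in the observed ICG rate from one miscoded event, 1/n: 1/75 = 1.3 percentage points, 1/226 = 0.44, 1/413 = 0.24.
- Genuine ICG events expected in 75 patients at the 1% bound: 75 × 0.01 = 0.75.
- Chance of at least one genuine event at that bound: 1 − 0.99^75 = 53%.
- One-sided 95% upper limit with no events in 75 patients: 1 − 0.05^(1/75) = 3.9%.

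The dual-tracer cohort would thus be expected to show about one genuine ICG event or none, and one miscoded event would exceed the expected count of 0.75. The expected number of miscoded events would require a radiocolloid reaction rate, which the documents do not give. I have not assumed one.

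**The case against.** The strongest reply is that this is loose wording and that no loss of data has been shown. Both tracers are given immediately before surgery, so the unprotected interval is probably short. The Section 7.0 table separately requires intraoperative adverse events to be recorded, with no restriction to ICG. Table 10.1 is a log of events before docking, a period that includes the interval. Section 8.0 puts every included patient in the safety evaluation. Most of this stands: it limits the consequence but does not reconcile the passages or give the radiocolloid a category.

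Three stronger readings are tempting, and the documents do not support them.

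- **A reader might infer that radiocolloid reactions are either missed or charged to ICG.** There are other outcomes. An event after ICG is logged whatever its attribution and can be graded Unlikely or Unrelated, or logged under the sentinel node procedure. Miscoding to ICG is possible but not inevitable.
- **A reader might infer that a radiocolloid signal cannot reach the Safety Monitoring Committee unless it is life-threatening or fatal.** Section 10 also sends the committee serious events related to the sentinel node procedure, and all serious events go to the study coordinator. What is missing is a designated route.
- **A reader might infer that expectedness is judged against the ICG insert.** The definition refers to the package insert or manufacturer's instructions and names no product. The plan leaves this open.

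It is also fair to say that 1/75 is the weight of any single event, genuine or miscoded, so the arithmetic shows sensitivity to one error and does not demonstrate bias. An extra form column will not always settle which of two agents, given close together, caused a reaction. It will at least let the investigator's judgement be recorded.

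**Conclusion.** The point holds as a minor defect in the current text. The written capture window starts at the second of two injections in at least 75 patients, conflicts with the plan's own definition of an adverse event, and has no start if radiocolloid alone is continued. Reactions that are captured cannot be identified as radiocolloid reactions. Some may be coded to ICG, which blurs the ICG-complication estimate in dual-tracer patients by 1.3 percentage points per event in 75 patients, or 0.4 in 226.

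This rests on reading the study drug as ICG only, as the Section 10 heading has it, and on the stated order of injection. The number of events affected is unknown, since neither a radiocolloid reaction rate nor the interval between injections is given. Sensitivity, negative predictive value and the two-stage design are not touched.

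**What to change.** 1. In Section 7.0, in the ICG adverse-event paragraph of Section 10 and in the title of Table 10.1, start capture at the first injection of any tracer. This resolves the conflict with the general definition and covers the radiocolloid-alone branch.
2. In the attribution scale and on the SAE form, add the radiocolloid as a separate attribution target beside ICG. State that expectedness is judged against the relevant product's own insert.
3. Record the injection times of both tracers.
4. Report ICG-related adverse events overall and separately for dual-tracer and ICG-only patients. State in advance that no ICG-only estimate will exist if the combination or radiocolloid alone is continued. For that reason the ICG-only group cannot be made the sole basis for the objective.

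The cost is revised wording and one extra column on the logs and SAE form, with the second injection time as one more entry. No visits, staff or patients are added.

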#### 8.0 EVALUATION CRITERIA

-Technical success rates, sensitivity and false negative rates with ICG and Tc99 nanocolloid will be compared per patient, per hemipelvis and per pathway, UPP and LPP.

- All patients who are injected with tracer and not converted to open surgery before detection and removal of SLN's will be included for evaluation of technical success rate (described per patient, per hemipelvis and per separate pathway) after first and in case of non-dispay of any of the LPP and UPP after reinjection of ICG as described.

- Patients with at least one SLN type1-2 identified will be included for determining the sensitivity and the negative predictive value for the SLN ICG concept. In addition the overall SLN concept, including SLN macro will be evaluated as of above.

- All patients included, regardless of conversion to open surgery and mapping of ICG (or the combination of ICG and Tc99 nanocolloid) will be included in the evaluation of feasibility and safety.

- Intraoperative adverse associated with the detection and removal of SLN will be evaluated and reported separately on all patients who have at least one SLN removed regardless of type, i.e all patients in whom SLN were removed separately.

- Postoperative complications until 30 days after surgery will be reported.

-The incidence of lymphatic complications defined by the questionnaire will be evaluated

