#### 4.0 STUDY MODALITIES

#### **Surgical Procedures**

Patients with stage 1a2- 2a1 cervical cancer planned for primary surgery with either a Querleu-Morrow B2- C2 radical hysterectomy or a robotic radical trachelectomy.
Injection of tracer (a total of 80 MBq Technetium nanocolloid and 2,5mg ICG solution / 2,5 mg/mL) will be injected submucosally into the cervix ad 2-4-8-and 10 O'clock respectively at onset of surgery (first 75 patients).

- Scanning of pelvic side walls after a minimum of 20 minutes after injection and a transperitoneal or retroperitoneal evaluation of ICG uptake per pathway (UPP and LPP bilaterally)

- Detection and removal of SLN will follow a strict protocol with a proximal- presacral dissection before the distal external iliac-obturator nodal compartment dissection and with careful opening of the presacral, paravesical and pararectal planes to avoid leaking of tracer. SLN will be defined as describe below.

- Identified SLN's and the upper paracervical tissue will be sent for frozen section and further for final ultrasectioning and immunohistochemistry as described below.

- A full pelvic nodal dissection will be performed after the removal of SLN's.

- The described procedures in this protocol will be performed with robot-assisted laparoscopy and with removal of SLN and non-SLN's before the radical hysterectomy/ trachelectomy.

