#### Injection of Indocyanine Green (ICG)

- The ICG is prepared by thorough mixing of 10mL of sterile water with the lyophilized ICG in its vial creating a 2.5mg/mL concentration. The lot number, expiration date and dose injected (mg) will be recorded.

- Six separate sterile 1mL syringes is prepared with 0.25 mL ICG solution (0.625 mg ICG)in each syringe is prepared.

- A 0.6x38 mm 23G needle is attached to each syringe for the injection. A separate back table is used for the syringes.

- The ICG injection will be performed immediately before placement of surgical port and docking the robot.

- Half the ICG volume in each syringe is injected submucosally and half the volume 3 cm into the cervical stroma at 2-4-8-and 10 O'clock respectively to a total dose of 2.5mg ICG and a total volume of 1 mL. Time for injection is recorded.

- After injection of dye, a fornix presenter without an intracervical device is placed

- A second ipsilateral injection of 0,25mL ICG is performed in case of non-display of

either of the upper (UPP) or lower (LPP) paracervical pathways after a minimum of 10 minutes observation time after ICG injection. The injection is done at 3 and 9 O'clock respectively, half the volume submucosally and half the volume 3 cm into the cervix. - Display of the separate lymphatic pathways (UPP, LPP and IPP will be recorded after the first and if performed after the second injection).

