#### **Sentinel Node Identification**

The bilateral technical success rate of SLN identification is important to determine if this technique can be transferred to clinical practice. Previous studies at our institution using Technetium  Nanocolloid as single tracer have shown a bilateral mapping rate of 65% in tumors smaller than 20 mm and in all size cervical cancer of 59%. Based on pilot studies at our institution on cervical and endometrial cancer with the use of ICG we expect that the bilateral pelvic SLN identification (defined as at least one SLN per hemipelvis) will be 90% or more: We intend to separately study if reinjection of ICG will enhance the bilateral detection rate. A lower bilateral detection rate will lead to the need of full lymphadenectomy in a higher proportion of patients.

A clear anatomically definition of what is a SLN and a strict surgical algorithm as described in this study is important.

Importantly, accreditation of surgeons will be performed as described and is likely important to achieve a similar success rate as in pilot studies.

**The sentinel nodes** are defined as the juxtauterine ICG positive / radiopositive node with an afferent ICG positive lymphatics in each of the UPP and LPP respectively on each pelvic side with the potential of parallel lymphatics in the UPP to the external and obturator areas . These SLN are defined as **SLN type 1.** 

In case of a ICG positive lymph vessel where no nodes are ICG positive in that pathway, the node where the ICG positive lymphatic channel ends is defined as **SLN ICG type 2**. The definitions based on ICG positive lymphatic channels were only attributed for nodes defined by ICG but does not exclude that nodes were also defined by radiopositivity. Nodes macroscopically suspect of metastatic disease will be defined as **SLN Macro** regardless of ICG uptake or radiopositivity but with information on ICG and radiopositivity.

Importantly, to secure accuracy, the positions and types of SLN will be marked on an anatomical chart, recorded on a list with anatomical locations and placed in pre-labeled jars with corresponding names and numbers. The SLN will be defined as **SLNICG**,

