**SLNICG+Radio**, and **SLNRadio** and for SLN defined by ICG also as type 1 and 2. This list is used by the department of pathology for reporting the results to minimize the risk of errors in location of nodes and which nodes are SLN's, the types of SLN as of above and non-SLN's. A copy of the list is kept in the patients study file. Nodes defined as SLN will have red labels on the jars, other nodes will have black labels.

SLN's will be sent for frozen section and final histological evaluation including ultrasectioning and immunohistochemistry as described. SLN's will be sent for frozen section during surgery for intraoperative decisions on the extent of lymphadenectomy (paraaortic or not), transposition of ovaries and abortion of the hysterectomy in favour of radiochemotherapy..

[figure not shown]
Before final removal of SLN, the pelvic side walls will be scanned with the gamma-probe to get an overview of radiopositivity per hemipelvis including the presacral area. After opening of the avascular planes as of below a renewed scanning with the probe will be performed. Finally, in case no SLN radio have been identified per pathway, a final scan with the probe will be performed after removal of SLN's. The display of ICG in the respective pathways will be evaluated a minimum 10 minutes after the injection of ICG, first transperitoneally, and if not seen, after opening of the retroperitoneal avascular planes

starting with the presacral plane, then the paravesical and pararectal planes leaving the lymphatics intact with the aid of switching between white light and the ICG mode (Firefly mode). In case of a non-display of a pathway an ipsilateral injection of ICG as described will be performed. (the comparison of bilateral mapping rates between ICG and radiotracer will be performed before any second injection of ICG). Another 10 minutes will be alloved for awaiting distribution of ICG in the respective pathways. To minimize disturbance by leaking ICG or radiotracer identification and removal of SLN's starts cranially, presacrally (along the LPP) and continues at the pelvic side walls along the UPP. After removal of SLN's the upper lymphovascular parametrial tissue is removed separately (defined as the tissue along the uterine artery, medial to the obliterated umbilical artery and caudal of the supravesical artery) as it may contain lymph nodes that may not be separated from the green lymphovascular tissue and hence be the juxtauterine lymph node.

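### The planned before/after rates cannot separate the effect of ICG reinjection from the extra waiting time; recording times and wording the result accordingly would be a cheap improvement

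*Combined protocol and SAP*

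**What the plan says.** Section 1 lists a separate objective: "To estimate if reinjection of tracer (ICG) will enhance the technical success / bilateral mapping rates". Section 4.0, Sentinel Node Identification, repeats it: "We intend to separately study if reinjection of ICG will enhance the bilateral detection rate".

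The only analysis tied to this objective is in Section 8.0. It evaluates technical success per patient, per hemipelvis and per pathway, "after first and in case of non-dispay of any of the LPP and UPP after reinjection of ICG as described", in all injected patients not converted to open surgery before SLN removal. Section 11 gives no comparator, test or threshold for it.

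The procedure that produces the two readings is as follows:

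- **Trigger.** Section 5.0: "An ipsilateral reinjection of ICG will be performed in case of non-display of either of UPP or LPP". The injection section of 4.0 places this "after a minimum of 10 minutes observation time after ICG injection".
- **Second reading.** Sentinel Node Identification: "Another 10 minutes will be alloved for awaiting distribution of ICG in the respective pathways".
- **Record.** The anatomic plan in Section 4.0 has display boxes after the first and after the second injection, and a reinjection yes/no box. The time of the first injection is recorded. The documents show no field for the time of a reading, of the reinjection or of later display.
- **Tracer comparison.** Sentinel Node Identification states that ICG and radiotracer bilateral mapping rates are compared before any second ICG injection.

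**The concern.** The objective asks what the second injection does. The analysis shows what happens between two readings, and two things change between them: a second dose is given, and the first dose has more time to travel. No group is observed for the same extra time without reinjection, so a pathway that would have filled late anyway is counted as a success of the second dose.

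What is at stake is the wording of one secondary conclusion. Section 2 already attributes the pilot rise in technical success, to around 95%, to reinjection. Without times on record, this trial could repeat that attribution but could not examine it. Times not noted during surgery are hard to recover later.

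**Working it through.** **1. Can the second rate fall?** A pathway displayed at the first reading is counted as a success and stays one. Only a non-displaying pathway can change status, and only from failure to success. The second rate is therefore at least as high as the first, whatever reinjection does.

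**2. How much extra time does the first dose get?** The minimum before reinjection is 10 minutes and another 10 are allowed afterwards, so the first dose has had at least 10 + 10 = 20 minutes by the second reading. Section 4.0, Surgical Procedures, also has "Scanning of pelvic side walls after a minimum of 20 minutes after injection". This does not match the 10-minute reading that triggers reinjection.

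**3. How large could the spurious gain be?** The plan gives no figure to reproduce. It states neither the first-injection ICG non-display rate nor a late-display rate, so both are assumed here.

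- N = 226, the stage 1 total in Section 11.
- Share of patients reinjected, assumed 10%, 20% or 35%: 226 × 0.10 ≈ 23, 226 × 0.20 ≈ 45, 226 × 0.35 ≈ 79 patients (n).
- Proportion of reinjected patients in whom the first dose alone would fill late, assumed q = 2%, 5% or 10%.
- The second injection is taken to have no effect at all.

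Expected spurious gain = n × q / 226, in percentage points:

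| n reinjected | q = 2% | q = 5% | q = 10% |
|---|---|---|---|
| 23 | 0.46/226 = 0.2 | 1.15/226 = 0.5 | 2.3/226 = 1.0 |
| 45 | 0.9/226 = 0.4 | 2.25/226 = 1.0 | 4.5/226 = 2.0 |
| 79 | 1.58/226 = 0.7 | 3.95/226 = 1.7 | 7.9/226 = 3.5 |

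The gain is linear in q, so other assumed rates can be scaled from the table.

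**4. Why this is an upper bound for bilateral mapping.** The table treats every reinjected patient as a bilateral failure at the first reading. Reinjection is triggered when either the UPP or the LPP is dark, whereas bilateral mapping needs only one SLN per hemipelvis. A patient reinjected for a dark LPP may already be mapped on both sides, and late filling then leaves the bilateral rate unchanged.

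**The case against.** **The cumulative rate is the useful quantity.** Sections 2 and 4.0 care about how many patients would need a full dissection because mapping failed. A pathway that fills late from the first dose is still mapped, so the overall technical success rate is not overstated. This stands. Only the attribution to the second dose is in doubt.

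**The plan has no rule to break.** A reader might infer that the trial is bound to declare reinjection effective even if it did nothing. The documents do not support that: the objective is one of estimation, and no test, alpha or criterion for enhancement is stated. Rejection rates for a paired test would describe a test that is not in the plan. Nor does a high chance of some gain mean a large one. With 45 reinjected patients and q = 5%, the chance of at least one conversion is 1 − 0.95^45 = 90%, but one conversion is 1/226 = 0.4 points.

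**There are partial safeguards.** Ten minutes is a minimum. ICG is injected before port placement and docking, and a pathway not seen through the peritoneum is looked at again after the retroperitoneal planes are opened, before reinjection. This probably makes late filling less common. It does not exclude it, and without recorded times nobody can show how long each pathway had been dark.

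**The obvious remedy is incomplete.** Newly mapped over reinjected has the same numerator as the before/after difference and credits late filling in the same way. It can already be derived from the display chart. This also stands, which is why the times and the wording matter more than the ratio. The data forms that Section 7.0 places in Appendix A are not shown, so some time fields may already exist.

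**Conclusion.** The point holds as a cheap improvement to a secondary estimation objective. As planned, the two rates describe the strategy of injecting, waiting and reinjecting. They cannot show that the second injection itself enhances mapping, because extra time and second dose go together and there is no unreinjected comparator.

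The size of the bias is unknown. The range of about 0.2 to 3.5 percentage points rests entirely on the assumed reinjection shares and late-filling rates, and is an upper bound for bilateral mapping under those assumptions.

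A reader might also infer that the trial's main results are compromised. They are not. The main endpoint in Section 11 is per-patient sensitivity and false negative rate / negative predictive value, which does not depend on which dose displayed a pathway. The tracer comparison of bilateral mapping is made before any second injection.

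**What to change.** In Section 8.0 and on the existing display chart:

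1. Record the time of the last reading before reinjection, of the reinjection, and of first display afterwards. The first injection time is already recorded.
2. Report newly mapped over reinjected with exact 95% confidence intervals per pathway, counting pathways still dark at that last reading. Report separately per hemipelvis and per patient among those not yet mapped at that reading. Show each by time since first injection.
3. Do not test the after-second rate against the after-first rate. Keep the cumulative rate as the description of the whole strategy.
4. State the gain as that of reinjection plus further waiting. Treat the results by time as supportive only, since they too have no unreinjected control.

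The 10-minute and 20-minute passages in Section 4.0 should be reconciled. No waiting time or dose is proposed here.

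The cost is two or three time entries during surgery and a short change of wording, with no extra patients or procedures. The downside is a less favourable and less causal statement of the reinjection benefit, based on the smaller reinjected group.
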